2.2.1 Secondary Objectives

1. To compare the proportion of patients with virological suppression at 24 months in patients receiving care via community ART models with those receiving care in the clinic (standard of care).

2. To compare Loss to Follow-up (LTFU) rates and missed dispensation of ARVs among individuals receiving care via community ART models with those receiving care in the clinic (standard of care), measured using routine health centre data

3. To compare HIV disease progression, and death among individuals receiving care via community ART models with those receiving care in the clinic (standard of care), measured using:

- CD4 cell count, WHO staging events, death from routine health centre data.

4. To qualitatively assess how health staff (including CHiPs) and PLWH on treatment experience the two models of care. This would be achieved through:

- Documenting treatment, adherence and retention experiences of PLWH accessing treatment through adherence club and home delivery models;

- Exploring the impact of the two models of care on access to treatment, adherence and retention according to the experience and perspectives of CHiPs and health facility staff;
- Qualitatively comparing how participant (PLWH and health staff) experience the models of care and experiences with the routine standard of care at the local health facilities;
- Qualitatively assessing participant (PLWH and health staff) perceptions about and experiences with the impact of the models of care on HIV services at the local health facilities.

5. To measure the health system costs of delivering the different community ART models.

In addition, we will measure the effect of the combined models on health facility crowding and waiting times as well as time to ART initiation of new patients in the 2 facilities (non- randomised comparison as both facilities have all models of care).

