4.0 Study Outcomes

The primary and secondary objectives for this study are listed in Section 2.2. The outcome measures for these objectives are listed below and will be measured in all study arms unless otherwise noted.

A. Primary Outcome – viral suppression at 12 months measured using the standard of care viral load testing equipment currently in place. Viral suppression will be defined according to National guidelines

B. Secondary Outcomes - these will include:

1. ***Viral suppression at 24 months*** – undetectable HIV viral load 24 months after entry into the models of care. This will be done as part of routine laboratory monitoring and measured using routine programmatic data.

2. ***Retention in care / Loss to Follow-up*** -Loss to follow-up from ART programmes describes all patients who are no longer in care and have an unknown outcome. A most useful definition of “loss to follow-up” should refer to patients with unknown outcomes(49). For this study, LTFU will be defined as “*no patient contact for 90 days or longer after the last given appointment*”.

Retention in care refers to *all patients retained in the HIV program*. Patients who are no longer retained in care with unknown outcomes will be classified as LTFU.

- In this study, retention will be defined as the number (%) of clients who are retained in the program at 6, 12 and 24 months after implementation of the intervention.
- The time to Lost to follow-up will be calculated in months according to the time interval between the dates of entry into the intervention to drop out, as recorded in the routine programmatic data.
- Proportion of patients that returned to mainstream care at 6, 12 and 24 months.

3. **HIV disease progression** – defined as having a new or recurrent WHO stage 3 or 4 condition after 6 months of ART, or a fall in CD4 count, (1). For patients with baseline CD4 count of < 200 cells/ μ l a fall of CD4 count to baseline or below after 6 months of ART; or persistent CD4 count < 100 cells/ μ l after 6 months of ART. (2). For patients with baseline CD4 count \geq 200 cells/ μ l, a persistent decline in CD4 count after two or more tests. For this study we will determine the following using routine health centre data:

- Proportion of patients who have had their CD4 count tests done at 6, 12 and 24 months after entering the models of care
- Proportion patients who developed a WHO stage 3 or 4 condition at 6, 12 and 24 months

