- Proportion of patients with CD4 count below 200 at 6, 12 and 24 months despite on treatment.

4. Death – defined as death at any point during the intervention due to any HIV related cause after enrolment into the study.

5. Participant choice of model and retention within that model. The following outcomes will be measured using programmatic and routine health centre data:

- Proportion of patients who enrolled into the models of care by sex
- Proportion (%) of eligible patients but refused to enter the model of care at baseline
- Proportion of patients who switched back to mainstream care at 6, 12 and 24 months and reasons for switching
- Number of club sessions and home visits that took place at 12 and 24 months after start of intervention

6. Drug Supplies –using routine health centre and programmatic data, we will determine:

- Number of groups/individuals missing at least one refill in the last 12 and 24 months (ART, Cotrimoxazole)
- Missed dispensations of ARVs at 6, 12 and 24 months.
- Proportion of pre-packed drugs returned to the clinic after a club session or home-based visit.
- Number of reported cases of ART drugs being pilfered after the start of the intervention.

7. Qualitative evaluation- of the acceptability and functioning of the two models of community ART delivery based on systematic structured observations of delivery, in-depth interviews and focus group discussions with key-informants (CHiPs, health facility staff) and longitudinal interviews with PLWH.

8. Economic Analysis – this will include:

- Measuring and comparing the incremental costs of the two intervention packages. The economic analysis will focus on measuring economic costs of the interventions from provider's perspective. The main focus will be on costs to the health services, including personnel, equipment and materials. The incremental cost of the interventions will be estimated by comparing costs of service provision and healthcare utilization with non-intervention healthcare facilities.
- Measure the impact of implementing the community ART delivery models on health systems and service delivery at local health centres in terms of technical and allocative efficiency of available HIV resource.

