5.0 Data Collection and Tools

Data will be collected at the following points:

Baseline

Three (3) months

Six (6) months

Twelve (12) months

Twenty four (24) months

Routine data will be collected using the national HMIS system and patient clinic records. At baseline, the following variables will be collected from patients to determine their influence on the outcomes:

- Age, sex, weight
- Recent CD4 count before enrolling into the models of care
- Viral load
- WHO stage at enrolment
- Date of starting ART
- Current drug regimen.

To maximize the validity of this information, the study team will work closely with the health centres to improve the collection and management of these routine data.

Data captured from the community models of ART delivery will be collected using the same hand held collection device being used in the main HPTN trial. A specific programme for this model will be installed in the device. This program is designed to maximize the quality of data collection using drop down lists and incorporating checks to avoid simple data entry errors. The CHiPs will undergo formal training on how to use the software to capture data at community level and sync it with the facility database and this training will be documented and retained in the site files.

Under the leadership of the Zambian Ministry of Health, the community ART steering committee has agreed upon a set of core indicators to be used to monitor and evaluate the community ART service delivery models being piloted by different partners. To facilitate the collection of the key indicators across both models, a list of common indicators will be used and this will be captured from both smart care and routine programmatic data.

Appendix 2 gives a detailed description of the data captured by the Chips in both Adherence clubs and home-based visits. The EDC program will capture data as required by the National ART community module for stable on care patients which has been developed by EGPAF and implementing partners. The following data will be captured in the device during the community ART model visits:

At clinic level:

- Patient ART registration details- Name, Sex, Age, ART number

At community Level (Adherence Clubs and Home based Visits)

- Date of visit
- Symptom Screen (fever, weight loss, cough, headache)
- Pregnancy screening for females
- Adherence counselling and types of counselling
- Pre-packed drugs dispensed
- Services referred for PMTCT, ART, STI, VMMC, etc.

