- Next community and clinic visit appointment

Data captured electronically during community visits will be linked to the HIV care databases at the health centre. The study team will work closely with the Ministry of Health and implementing partners

supporting the sites to collect relevant data from both the supply and demand side. Data that will be captured electronically during the club and home visits will be synced at the end of the day with the health care centre database. This is to ensure that indicators used for routine monitoring and follow-up will be entered in the current smart care system at facility level. The table below summarizes the core indicators that will be collected at both facility and community levels for the purpose of monitoring and evaluation.

Table 6: Common indicators for community ART models

Common Indicators for Community ART Models of Care		
Main	Core Indicator	Data Source
1. Recruitment	Proportion of patients enrolled into Home-Based ART models by sex	Smart care / HMIS
	Proportion eligible but refused	Consenting register
	Proportion of patients dropping out (within 1,3,6 and 12 months)	Routine data/ Programmatic data
	CD4 count at enrolment	Smart care
	Time on ART before enrolment	Smart care
2. Retention	Number (%) of clients retained at 1,3,6,12 and 24 months	Smart care
	Loss to follow up by reason:	Smart care
	
 • Dead • Transfer • Lost 	
	Number of patients returned to mainstream care (@ 3, 6, 12, 24 months)	Smart care
3. Laboratory	% of clients who developed an OI @ 3, 6, 12 and 24 months	Smart care and routine programmatic data
	Proportion of patients who have had viral loads within the last 6 months	Smart care and routine programmatic data
	Proportion of patients who have had CD4 count in the last 6 months	Smart care and routine programmatic data
	Proportion of patients with viral suppression at 12 and 24months	Smart care and routine programmatic data
4. Drug Supplies	Proportion of patients with CD4 count below 500 in the last 12 months despite treatment	Smart care and routine programmatic data
	Number of individuals missing at least one refill in the last 6 and 12 months	Smart care and routine programmatic data

Additional data collected for measuring the outcomes of the study objectives will be collected from patient clinical records. The key clinical indicators will be collected from smart care and HMIS and these includes:

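### The one CD4-level measure listed in Section 4.0 B.3 is the share below 200, which uses no baseline and does not match that section's own change-based definition of progression

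*Protocol*

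**What the plan says.** Secondary objective 3 (Protocol Section 2.2.1) compares disease progression and death between community delivery and clinic care, measured by "CD4 cell count, WHO staging events, death from routine health centre data".

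Section 4.0 B.3 first gives a definition. Apart from new or recurrent WHO stage 3 or 4 conditions, progression is a CD4 fall:

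- baseline below 200: "a fall of CD4 count to baseline or below after 6 months of ART", or CD4 persistently under 100;
- baseline 200 or above: "a persistent decline in CD4 count after two or more tests".

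The same item then continues "For this study we will determine the following using routine health centre data" and lists three proportions: patients with a CD4 test done, patients with a WHO stage 3 or 4 condition, and "Proportion of patients with CD4 count below 200 at 6, 12 and 24 months despite on treatment". Only the third concerns the CD4 level.

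Section 5.0 collects "Recent CD4 count before enrolling into the models of care" among the baseline variables whose influence on the outcomes is to be examined. Table 6 in that section has a further row, "Proportion of patients with CD4 count below 500 in the last 12 months despite treatment", within a set introduced as "the core indicators that will be collected at both facility and community levels for the purpose of monitoring and evaluation". No mean, change or baseline-adjusted comparison of CD4 is named, and no CD4 mean, SD, margin or power is given.

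**The concern.** The definition and the list of measures do not fit together. Take a patient who enters at 550 and falls to 250. If the decline persists over two or more tests, this is progression under the definition, but it is no event on the listed measure. A patient who was already below 200 at enrolment and has since improved to 190 counts as an event on the listed measure, although nothing has fallen.

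Patients with a low baseline who meet the definition will indeed be below 200. The listed measure cannot tell them from patients who were always there.

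Entrants are virologically suppressed, on first-line ART for more than 6 months and in WHO stage I or II (Section 3.1.3). Few may therefore lie near 200, although the protocol gives no distribution. The hypothesis in Section 2.1 covers immunological outcomes and is one of non-inferiority. In that setting an insensitive measure is a particular weakness, because it makes an absence of difference easy to report.

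**Working it through.** **Plan figures.** No CD4 figure exists to reproduce. The primary-endpoint power in Section 7.0 does reproduce. Use variance per arm [p(1-p)/30 + k²p²]/(c-1), c = 34 and 35, true difference 0, margin 0.05 and z = 1.96. At p = 10% this gives 92.5% (k = 0.25) and 90.6% (k = 0.30), against the stated 93% and 91%. This supports using two-sided 5% and those zone numbers below.

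**Inputs.**
- From Section 7.0: 34 v 35 zones, 30 participants per zone.
- Assumed: CD4 measured in 40-80% of participants, so m = 12 to 24 per zone; gamma-distributed CD4 with SD 200; control mean 450 or 550; ICC 0.02; baseline-to-follow-up correlation r = 0.6 to 0.8; lower arm 30 cells lower on average; superiority test.

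**Effective sample size** = zones × m / [1 + (m-1) × 0.02].
- m = 12: design effect 1.22, giving 34 × 12/1.22 = 334 and 35 × 12/1.22 = 344.
- m = 24: design effect 1.46, giving 34 × 24/1.46 = 559 and 35 × 24/1.46 = 575.

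**Cut at 200.** Power = Φ(|p1 - p0|/SE - 1.96), with SE² = p0(1-p0)/n0 + p1(1-p1)/n1. The answer depends on how the 30-cell loss arises:

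| Form of the loss | Mean 450: share below 200 | Power, m = 12 to 24 | Mean 550: share below 200 | Power, m = 12 to 24 |
|---|---|---|---|---|
| All values scaled down in proportion | 7.3% v 9.2% | 14-20% | 1.2% v 1.6% | 7-8% |
| Mean lower, SD kept at 200 | 7.3% v 11.1% | 40-60% | 1.2% v 2.2% | 18-26% |
| Every patient loses 30 cells | 7.3% v 11.45% | 45-66% | 1.2% v 2.5% | 23-35% |

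Example (bottom row, mean 450, m = 12): SE = √(0.0734 × 0.9266/334 + 0.1145 × 0.8855/344) = 0.0223; 0.0411/0.0223 - 1.96 = -0.12; power 45%.

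**Baseline-adjusted CD4.** SE = 200 × √(1 - r²) × √(1/n0 + 1/n1).
- r = 0.6, m = 12: 160 × 0.0768 = 12.3; 30/12.3 - 1.96 = 0.48; power 68%.
- r = 0.8, m = 24: 120 × 0.0594 = 7.13; 30/7.13 - 1.96 = 2.25; power 99%.
- Without baseline (r = 0) the same formula gives 50-71%. Against the most favourable case for the cut at mean 450 (45-66%), most of the gain therefore comes from using baseline.

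**Loss confined to a subgroup.** Suppose 10% of one arm lose 150 cells, at mean 450. The mean difference is 15 cells, and the residual variance in that arm rises by 150² × 0.1 × 0.9 = 2,025.
- Cut: 25-38%.
- Adjusted mean: 22-34% at r = 0.6 and 35-53% at r = 0.8.
- At r = 0.6 the cut is slightly better; the adjusted mean is clearly better only near 0.8.

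**The case against.** The strongest reply is that B.3 does not reduce CD4 to a cut: its definition uses decline from the patient's own baseline. A statistical analysis plan, not shown here, could turn that into an analysis and add a continuous model. Baseline CD4 is also collected expressly to study its influence on outcomes, so it is not discarded. Much of this stands, and it rules out saying that the protocol knows CD4 only as a threshold. It does not remove the mismatch. B.3 itself says what will be determined, and nothing on that list corresponds to the falls it has just defined. Section 5.0 also mentions a proportion with continuous immunologic or virologic suppression, but it is again a proportion and carries no CD4 rule.

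A reader might infer that 200 in Section 4.0 and 500 in Table 6 are two values for one outcome, so that the result depends on which is chosen. The text does not support this. Table 6 holds common indicators agreed by the national steering committee for monitoring models piloted by several partners, over a different window. Section 5.0 describes data for the study outcomes separately. The trial outcome has one cut.

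A reader might also infer that the trial has little power for CD4. That cannot be derived from the document. Power of 14-20% and 7-8% for the cut arises only if the lower arm is scaled down in proportion. The hypothesis is also one of non-inferiority, with no CD4 margin stated. Borrowing the 5-point primary margin gives at least 91% for control shares of 1-10% (k 0.25-0.30). There the weakness would be a margin too wide for a rare event.

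**Conclusion.** The point holds in limited form. Section 4.0 B.3 lists a single CD4-level measure, which uses no baseline and does not match the progression definition above it. A baseline-adjusted comparison would use data already collected.

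For an average loss of 30 cells, power is about 14-66% for the cut at mean 450 and 7-35% at mean 550, against 68-99% for adjusted CD4. These figures rest wholly on assumed CD4 inputs and a superiority test, with the same design effect for both analyses. The gain is not universal: for loss in a small subgroup the cut can match or slightly beat the adjusted mean. Because the baseline is only a recent routine value with no stated window, the correlation could also be lower than assumed.

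This is a worthwhile refinement of a secondary outcome. It does not affect the primary analysis.

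**What to change.** In Section 4.0 B.3:

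- Add a between-arm comparison of CD4 count at 12 and 24 months (square-root scale if skewed), adjusted for baseline CD4 and community and allowing for clustering by zone.
- Keep the share below 200 as a descriptive figure.
- Make the listed measures match the definition, for example by listing the proportion who meet its CD4 criteria, and say whether baseline there means the enrolment value.

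In Section 5.0, state that the below-500 row of Table 6 is a monitoring indicator and not the trial outcome. The row itself need not change, since it is shared with other partners.

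The cost is a few lines of wording and one extra regression, with no new data. The downside is that a mean difference is less direct clinically than a percentage and less sensitive to loss confined to a few patients, which is why the percentage stays.

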Study Duration: The planned duration of the entire study will be approximately 24 months after implementation of the models. Assessment of the primary outcome is planned to be collected at 12 and 24 months after recruitment whereas secondary outcomes are planned to be collected at 6, 12 and 24 months after recruitment.

[figure not shown]
Primary Objective: To compare virological suppression at 12 months in HIV + patients receiving care via community ART models with those receiving care in the clinic (standard of care).

Secondary Objectives:

1. To compare the proportion of patients with virological suppression at 24 months in patients receiving care via community ART models with those receiving care in the clinic (standard of care).
2. To compare Loss to Follow-up (LTFU) rates and missed dispensation of ARVs among individuals receiving care via community ART models with those receiving care in the clinic (standard of care), measured using routine health centre data
3. To compare HIV disease progression, and death among individuals receiving care via community ART models with those receiving care in the clinic (standard of care), measured using:
 - CD4 cell count, WHO staging events, death from routine health centre data.
4. To qualitatively assess how health staff (including CHiPs) and PLWH on treatment experience the two models of care. This would be achieved through:
 - Documenting treatment, adherence and retention experiences of PLWH accessing treatment through adherence club and home delivery models;
 - Exploring the impact of the two models of care on access to treatment, adherence and retention according to the experience and perspectives of CHiPs and health facility staff;
 - Qualitatively comparing how participant (PLWH and health staff) experience the models of care and experiences with the routine standard of care at the local health facilities;
 - Qualitatively assessing participant (PLWH and health staff) perceptions about and experiences with the impact of the models of care on HIV services at the local health facilities.
5. To measure the health system costs of delivering the different community ART models

Study Sites: This study will be implemented in two Lusaka communities – Chipata and Kanyama.

OVERVIEW OF THE STUDY DESIGN AND RANDOMIZATION SCHEME

[figure not shown]

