7.0 Statistical Analysis

The analysis will compare each of the two trial intervention arms with the “standard-of-care” (control arm), and the primary endpoint is viral suppression at 12 months after study enrolment. The analysis will be done using standard methods for a cluster- randomized trial with a non-inferiority design.

The study has been designed to a study power of between 73 -94% to demonstrate that a trial intervention arm is not inferior to the “standard-of-care” arm for the percentage of participants who are virologically suppressed at 12 months after study enrolment. The definition of “not inferior” is that the percentage of study participants who have died, or are alive but not virally suppressed, at 12 months after enrolment in a trial intervention arm is $\leq 5\%$ higher than in the standard-of-care arm.

Based on the data from the annual first round of the CHiP intervention in the main trial, the number of adults who are known by the CHiP teams to be HIV-positive and to be taking ART at the time of the most recent CHiPs follow-up visit averages approximately 50 per zone, with a harmonic mean of approximately 36 per zone. Assuming that 80% of such adults agree to participate in the study and have not moved out of the community within 12 months after enrolment, the number of study participants per zone who can contribute to the primary endpoint measurement will have a harmonic mean of approximately 30.

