Study power calculations have been done with the assumption that an average of 30 study participants per zone will contribute to the measurement of the primary endpoint; that 35 zones are randomized to the 2 intervention arms and 34 zones to the “standard-of-care” arm; and that among study participants in the “standard-of-care” the percentage who have died, or are alive but *not* virally suppressed, 12 months after enrolment to the study is in the range 10-15%. It is also assumed that the coefficient of variation k , of the variation across zones in the percentage of study participants who have either died or are alive but *not* virally suppressed at 12 months after study enrolment, is in the range 0.25 to 0.3. If the percentage of participants who have died or are alive but are *not* virally suppressed at 12 months after study enrolment is 10% in the “standard-of-care” arm, and $k=0.25$ or $k=0.3$, study power is 93% and 91% respectively to show that a trial intervention arm is not inferior to “standard-of-care”. The corresponding study power figures are 78% and 74% if the percentage of participants who have died or are alive but are *not* virally suppressed at 12 months after study enrolment is 15% in the “standard-of-care arm”.

Table summarising study power to show that community ART provision is not inferior to standard-of-care, in terms of patient viral suppression 12 months after either enrolling into community ART or continuing with standard-of-care at the clinic

Standard of care, % not virally suppressed at 12 months after enrolment	Intervention, % not virally suppressed at 12 months after enrolment	Coefficient of variation k	Number of participants per cluster	Study power (%)
5%	$\leq 10\%$	0.25	30	99%
10%	$\leq 15\%$	0.25	30	93%
15%	$\leq 20\%$	0.25	30	78%
5%	$\leq 10\%$	0.30	30	99%
10%	$\leq 15\%$	0.30	30	91%
15%	$\leq 20\%$	0.30	30	74%

We will also use qualitative and quantitative methods to evaluate the acceptability and feasibility of the two models of ART delivery and the barriers to access in care. Interviews would look at the trajectory of linking to care, reflecting on the HIV pathways and care choices prior to the intervention and after and exploring their comparative experience with satisfaction of care and

patient rights, HIV related stigma, household and other social relationships, livelihood pursuits and wellbeing.

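### Section 4.0 counts only HIV-related deaths, against objective 3 and the primary failure definition, and times several secondary outcomes from model entry or implementation instead of recruitment

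*Protocol*

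**What the plan says.** **Death.** Protocol Section 4.0 B.4 gives the secondary outcome as "defined as death at any point during the intervention due to any HIV related cause after enrolment into the study". Secondary objective 3 (Section 2.2.1, repeated in the Protocol Summary) reads "To compare HIV disease progression, and death among individuals receiving care via community ART models", to be measured using "CD4 cell count, WHO staging events, death from routine health centre data". Neither phrase limits the cause. Section 7.0 defines non-inferiority through "the percentage of study participants who have died, or are alive but not virally suppressed, at 12 months after enrolment", again without regard to cause. Table 6 in Section 5.0 lists death as one of three reasons for loss, taken from Smart care, with no entry for cause.

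**Time origin.** The Protocol Summary, under Study Duration, states that "secondary outcomes are planned to be collected at 6, 12 and 24 months after recruitment". Section 4.0 opens by saying that the outcome measures "will be measured in all study arms unless otherwise noted". Within Section 4.0, 24-month suppression (B.1) and the proportion with CD4 tests done (B.3) run from entry into a model of care. Time to loss to follow-up (B.2) runs from entry into the intervention, and retention (B.2) from its implementation. For the 12-month endpoint, Section 7.0 says that "the primary endpoint is viral suppression at 12 months after study enrolment", and the caption of its power table gives "12 months after either enrolling into community ART or continuing with standard-of-care at the clinic".

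**The concern.** A death from a cause unrelated to HIV in the first 12 months would be a failure on the primary endpoint but would not count as a death in the secondary outcome. The death comparison would answer a narrower question than objective 3 asks, and it would need a judgement on cause that the Protocol does not describe. Participants are told their allocation (Section 3.1.5), and no masking of whoever might classify deaths is mentioned.

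A randomised comparison also needs one clock that starts in the same way in every arm. Entry into a community model is a choice. Under Section 3.1.5, participants in the intervention arms may decline it, take it up later or leave it. If the clock starts at entry, its meaning is unclear for controls and decliners, and for a late joiner it starts at a decision made after randomisation. Implementation has a different problem: it is a programme date, not a date belonging to the participant.

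**Working it through.** **Step 1, the death definitions side by side.**

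| Place in Protocol | Cause of death counted | Start |
|---|---|---|
| 2.2.1, objective 3 | any | not stated |
| 7.0, primary failure definition | any | enrolment |
| 5.0, Table 6 | any (recorded only as dead) | not stated |
| 4.0 B.4 | HIV-related only | after enrolment |

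B.4 is alone in limiting the cause, and the data source that objective 3 names comes with no step for assigning it. B.4 does start at enrolment, so its fault is the cause limit and not the clock.

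**Step 2, the time origins in Section 4.0 B.1 to B.4.** Taking each separately listed time-bound measure:

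- Entry into the model or intervention: 24-month suppression, time to loss to follow-up, CD4 tests done (3).
- Implementation: retention (1).
- No origin stated: return to mainstream care, WHO stage 3 or 4 condition, CD4 below 200 (3).
- After enrolment: death (1).

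That is 3 + 1 + 3 + 1 = 8. The count depends on what is treated as an item. It leaves out the general definition of disease progression in B.3, which refers to time on ART. It shows only that the section mixes origins and does not measure impact.

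**Step 3, when the origins differ.** The schedule of visits in Section 3.1.2 puts enrolment into a club or home delivery at month 0, so for those who accept at once the two dates nearly coincide. They separate in two cases. The 6 months used below is an illustration; the Protocol gives no figure for delay.

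- Late joiner: someone who takes up a model 6 months after enrolment has 24-month suppression due, under B.1, at 6 + 24 = 30 months after enrolment. The Summary places that collection at 24 months after recruitment.
- Implementation clock: someone recruited 6 months after implementation has 24 − 6 = 18 months of personal follow-up at the 24-month retention point.

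**Step 4, whether the primary analysis is touched.** The power table in Section 7.0 can be reproduced. Inputs from that section are 34 control and 35 intervention zones, 30 participants per zone, a margin of 0.05, and k of 0.25 or 0.30. Two-sided alpha of 0.05 and no true difference are assumptions, since Section 7.0 does not state alpha. The variance per zone is v = p(1−p)/30 + k²p², the standard error is √[v(1/33 + 1/34)], and power is Φ(0.05/SE − 1.96).

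For p = 0.10 and k = 0.25: v = 0.003 + 0.000625 = 0.003625, SE = 0.0147, and power = Φ(1.44) = 92.5%, against 93% stated.

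The other rows give 99.8% and 99.8% (p = 0.05), 90.6% (p = 0.10, k = 0.30), and 77.7% and 73.3% (p = 0.15). The stated figures are 99%, 99%, 91%, 78% and 74%, so all agree within one percentage point. None of the inputs comes from B.1 to B.4, and the endpoint already counts any death from enrolment.

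**The case against.** The strongest reply is that the text can be read sensibly as a whole. Section 3.1.5 itself calls clinic care a model, the visit schedule puts model enrolment at month 0, and the power table caption treats joining community ART and continuing at the clinic as parallel starts. With a study planned for about 24 months after implementation, nobody can have meant a measurement at month 30. Deaths of any cause will be recorded anyway, and they count in the primary endpoint.

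Much of this stands. It means that the outcomes can be computed from enrolment and that the time-origin fault is one of contradictory wording. It does not cover late joiners or the implementation clock, the caption concerns the 12-month endpoint only, and elsewhere the models of care usually means the two community models. Recording all deaths does not alter the outcome that B.4 defines. An analysis plan could not settle the matter without departing from one section or another.

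Three stronger readings are tempting and are not supported:

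- A reader might infer that B.4 stops counting deaths once a participant returns to the clinic, because it refers to the intervention. Section 5.0 uses that term for a calendar period, and Section 8.2 keeps those who leave a model in the study, so the study period is the better reading.
- A reader might infer that controls have no usable clock. The wording is unclear, but a start at enrolment is available to every participant.
- A reader might infer that cause of death will be assigned with knowledge of arm and will favour one arm. The Protocol shows that participants know their allocation. It does not say who would classify deaths, so this is a possibility and not a finding.

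**Conclusion.** The concern holds for the secondary outcomes. B.4 is narrower than the objective it serves and than the primary failure definition, with no stated means of assigning cause. B.1 to B.3 use origins that conflict with the Protocol Summary and are not defined alike across arms. This should be corrected, but it does not threaten the main result: the primary endpoint and its power are unchanged.

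No size or direction of bias is claimed, because the Protocol gives neither the share of non-HIV deaths nor the number or timing of late joiners. The 30-month and 18-month figures rest on an assumed 6-month delay and are illustrations only. If nearly all participants accept a model at once and are recruited close to implementation, the origins will almost agree in practice; the limit on cause of death would remain.

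**What to change.** **Section 4.0 B.4.** Define death as recorded death from any cause, from study enrolment to 24 months, in all participants by randomised arm, including after return to clinic care. Keep HIV-related death as an additional descriptive outcome.

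**Section 4.0 B.1 to B.3.** Time every outcome that is compared between arms from the date of study enrolment, in all arms and whatever model is used. Return to mainstream care has no meaning for controls, so it should stay a descriptive outcome for participants who entered a community model.

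**Cost.** No new visits, tests or participants are needed, since enrolment and recorded deaths are already part of the planned data. It is nevertheless a change to a secondary outcome definition, so it needs a protocol amendment with the approvals described in Section 9.0. Section 4.0 treats participants lost to follow-up as having unknown outcomes, and no tracing of vital status is planned. Deaths in that group will therefore be incompletely captured, and the Protocol should state this as a limitation.
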